PCP Implementation Surveys: PCPs will receive surveys by email (through REDCap) every 6 weeks. Survey is expected to take 15 minutes to complete. For PCPs in the “all-in” arm, the first survey will be sent prior to the intervention “roll-out” and every 6 weeks after that. For PCPs in the “add-in” arm, the first survey will be sent prior to intervention A “roll-out”, intervention B “roll-out”, intervention C “roll-out”, and then 6 weeks after. The survey is created specifically for this study and focused on the acceptability of using the intervention component, feasibility of using the intervention component, the opportunity costs of using the intervention component (the time it takes to use the intervention, the perceived effect on other discussion topics with well child visits), and the intention and confidence (i.e. self-efficacy) to document and discuss NBS and SCT results.

PCP Qualitative Interviews: At completion of the Intervention period, PCP participants will be contacted to schedule the qualitative interview. Interviews will be expected to last ~30 minutes. Interviews will be completed over the telephone or using a video conferencing platform. If video conferencing is used, participants will be instructed to keep their camera turned off, so their image will not be recorded. The participant will be notified verbally when the recording has started and when it has stopped.

The qualitative interviews will assess their experience with the components and intention to document and disclose NBS/SCT results in the future.

Infant Identification:

Infants seen at a participating site during the retrospective and intervention period for a well child visit before 2 months of age will be identified through EHR data extraction on a rolling basis (i.e. once a month during the trial) based on ICD10 code for a new patient/well child exam (ICD 10: Z00.110, Z00.111, Z00.121, Z00.129, Z00.00, Z00.01 or CPT: 99381, 99382, 99383, 99384, 99385, 99391, 99392, 99393, 99394, 99395).

Documentation and Discussion of NBS/SCT results for all infants identified: via chart review. For each infant identified, the following data will be collected via EHR extraction and manual chart review:

- Email
- Preferred language
- MRN (to facilitate manual chart review)
- Gender
- Race, ethnicity
- Insurance
- Zipcode (to assess Childhood Opportunity Index)
- Phase of study they were first seen for a WCC (retrospective, “all-in” A/B/C, Intervention A, Intervention B, Intervention C)

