- Presence/absence of NBS
- Result of hemoglobinopathy NBS
- Presence/absence of NBS result documented in 1) problem list, 2) medical history, 3) progress notes
- Presence/absence of a disclosure conversation about NBS result in progress notes (including topics discussed: inheritance patterns, medical implications, reproductive implications, hematology/genetics consultation)
- Presence/absence of NBS results in After Visit Summary communication

Caregiver Survey from retrospective period:

Caregivers of three groups of infants will be surveyed if they are identified as speaking English (through EHR demographic data) and with an email address in the EHR:

- Group 1: All infants with SCT seen before 2 months of age within the 6 month retrospective period
- Group 2: All infants identified as Black or Hispanic seen before 2 months of age within the 6 month retrospective period

- Group 3: Infants seen before 2 months of age within the 3 month retrospective period and not included in group 1 or 2

Caregiver Survey during Intervention Period:

Caregivers from the participating office locations of three groups of infants will be surveyed if they are identified as speaking English (through EHR demographic data) and with an email address in the EHR:

- Group 1: All infants with SCT
- Group 2: All infants identified as Black or Hispanic
- Group 3: Infants seen in the first half of the month and not included in group 1 or 2

Caregivers will receive a survey at 2 and 6 months of age (+/- 1 month) delivered by email (through REDCap). Survey is expected to take less than 10 minutes to complete. Consent and survey responses will be obtained electronically. The survey will inquire about results of the NBS, preferences for information receipt, and satisfaction with well child visit.

Recruitment of Participants

- **See site selection under Study Procedures**

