(i.e. at start of the Intervention phase and then every month during the intervention phase) and NBS result reviewed if available in the EHR. Caregivers identified as speaking English (through EHR demographic data) and with an email address in the EHR will receive a survey at the start of the intervention phase if seen during the retrospective phase or at 2 and 6 months of age (+/- 1 month) if seen during the intervention phase. Email will be delivered through REDCap. Consent and survey responses will be obtained electronically.

- They will be told that participation is voluntary. They will be given the contact information for the PI and study coordinator for any questions or withdrawal from participation. The on-line survey will be ~5 minutes in length. Three follow-up requests will be sent to non-responders at ~1 week intervals. Responses will be collected within REDCap. Participants will be informed that completion of each survey will enter them into a lottery for a \$100 gift card. Twenty lottery gift cards will be given in total; 10 at 4 month intervals after initiation of the trial. Each caregiver that completes a survey will also receive a \$10 gift card.
- **Caregiver Survey Retention:** The only study procedure is completion of a 2 and 6 month survey. Each time the caregiver completes a survey they will be entered into a lottery for a \$100 gift card. Each caregiver that completes a survey will also receive a \$10 gift card.

Informed Consent/HIPAA Authorization

For PCPs: One consent form, called an information sheet, has been developed for this study that incorporates consent and HIPAA information. It has been designed to not require a signature. We are applying for a waiver of documentation of informed consent and HIPAA and alteration of consent. The phone numbers of the PI, research coordinator, and Nemours IRB are provided on the information sheet for potential participants to call or email with any questions that might arise regarding the research. This information sheet will be included in the REDCap survey link from the study team and attached to the recruitment email.

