We are requesting to waive a signature for consent, as the participants will be asked to document consent/assent via REDCap survey, and reaffirm consent/assent verbally prior to the qualitative interview. The surveys and qualitative interview presents no more than minimal risk to the participants. Additionally, we are not asking for any additional personal health information or identifiers apart from Greenphire information. The consent document would be the only other document connecting the survey responses and the PCP. The participants will be provided with an information sheet in recruitment emails and prior to starting the REDCap survey.

We are asking for a waiver of HIPAA authorization. The survey study involves no more than minimal risk to the participant. Additionally, the HIPAA form would be the only other document connecting survey response and the participant. Because we want the participants to be as honest as possible, we do not want the participant to feel that we can connect them to their responses and that connection could include the HIPAA documentation.

PHI will be used 1) to ensure eligibility of participants; 2) to contact for recruitment; and 3) to appropriately describe our sample. We will collect identifiable information (i.e. DOB and address) for those who receive a gift card to process study payment through Greenphire. This data will not be provided to or used for anything aside from payment. As this study will be conducted entirely remotely, it cannot be conducted without access to and use of PHI such as

Subject Completion/Withdrawal

contact information.

Subjects may withdraw from the study at any time without prejudice to their care or employment. The PI may withdraw a participant from the study if it is learned that they did not fulfill eligibility criteria. It will be documented whether or not each subject completes the study.

STATISTICAL CONSIDERATIONS

Evaluation of the Toolkit will focus on Proctor's framework of IS outcomes:⁴⁷

Primary Endpoint

- Penetration (via interrupted time series): via EHR extraction. Rate of scanned NBS results available in the EHR. Rate of documentation and disclosure of NBS and SCT result at < 2 months of age in each of the following: the problem list, the medical history section, and progress note. Evaluate monthly: retrospectively (pre intervention) and prospectively (post intervention).

Secondary Endpoint

- Acceptability: via PCP survey for each toolkit component.

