Sample Size Justification: This is a pilot study and there is no reported effect size on the intervention of this study in the literature. Therefore, the main goal of this study is to explore reliable effect size that would assist designing future studies with formal hypothesis testing. The primary aim of the study is to increase PCP's EHR documentation and disclosure of NBS and SCT carrier results during infancy (age less than 1 month). It has been found in a chart review that 71% of newborns over the last 3 years had a newborn screen result scanned into their chart. The goal of this study is to raise this to 90%. A sample size of 74 in each of the pre- and post-intervention period can detect the targeted difference in newborn screen of 19% with 86% power at the level of significance of 0.05. PCP documentation has been reported as 20% in the literature. We aim to raise this 50%. Again, a sample size of 43 in each of the pre- and post-intervention period would be adequate to detect the targeted difference in the PCP documentation with a power of 85% at the level of significance of 0.05. Currently 53% sickle cell traits has been documented. Once again, the goal is to raise this to 90%. A sample size of 21 infants with sickle cell traits (SCT) in each of pre- and post-intervention periods would be adequate to detect this difference in this documentation with a power of 80% at the level of significance of 0.05. In DE, the prevalence of SCT is 2.1% in overall children and about 7% in African Americans. Considering 2.1% SCT in overall children, we need 1000 infants to screen in each of the pre-and post-intervention periods, to detect the targeted difference with a power of 80% at the level of significance of 0.05. The study plans to recruit 10 PCPs in each of the intervention arm (20 PCP in both arms). About 6-10 infants are expected to be seen by a PCP in a month and 54-90 new infants are expected to be seen by a physician during 9 months of post intervention period. We expect that minimum of $540 \times 2 = 1080$ patients (540 for each intervention) to be seen by 20 PCPs. Therefore, a minimum sample size of 1080 infants is planned for each of the pre-and post-intervention periods for this study. The planned minimum sample size of 1080 in the post intervention period would also be adequate to determine the effect size for survey results and documentation and disclosures for each intervention arm separately.

Analysis of Qualitative Data:

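### SCT status is read only from the chart while the trial aims to raise scanning from 71% to 90%, so the denominator of the SCT documentation rate shifts with the intervention and its pre/post odds ratio is biased.

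*Combined protocol and SAP*

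**What the plan says.** Under Study Procedures, the paragraph on documentation and discussion of results states that for each infant "the following data will be collected via EHR extraction and manual chart review". The list that follows includes whether a newborn screen is present, "Result of hemoglobinopathy NBS", and whether the result is recorded in the problem list, medical history and progress notes. The caregiver recruitment text adds "NBS result reviewed if available in the EHR". No state laboratory link or other source independent of the chart is described.

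The primary endpoint, penetration, has as its first component "Rate of scanned NBS results available in the EHR". It also includes documentation and disclosure of newborn screen and SCT results before 2 months of age. No denominator is given for the SCT part.

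The Sample Size Justification reports that "71% of newborns over the last 3 years had a newborn screen result scanned into their chart" and continues "The goal of this study is to raise this to 90" percent. For SCT it says "Currently 53% sickle cell traits has been documented" and "Once again, the goal is to raise this to 90" percent, again without a denominator. It needs 21 SCT infants per period and obtains them as 2.1% of 1000 infants.

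Statistical Methods specifies a generalized linear mixed effects model with odds ratios. It gives no rule for infants with no result in the chart and no sensitivity analysis for them.

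**The concern.** An SCT infant with no newborn screen in the chart and nothing written about it cannot be recognised as having SCT, and so drops out of the denominator. An SCT infant with no screen in the chart but with the trait documented stays in and counts as a success. The described data can therefore only form an SCT rate over visible infants, and visibility is one of the things the toolkit is meant to change. Infants missed in the pre-period would enter the denominator in the post-period, so the two rates describe differently selected groups.

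The protocol's stated purpose is a reliable estimate of effect size for a later trial. More infants would not remove a bias of this kind. If the arms differ in how far scanning rises, the all-in versus add-in comparison of SCT documentation inherits it.

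**Working it through.** **The plan's own figures.** For 53% against 90%, 21 per period, two-sided 0.05, the arcsine formula gives 80.2% power (stated 80%). 21 / 0.021 = 1000 infants, and 20 PCPs × 6 infants × 9 months = 1080. These reproduce, but the step from 1000 infants to 21 treats every SCT infant as identified. If SCT could be recognised only from a scanned result, 1080 × 0.021 = 22.7 SCT infants would yield 22.7 × 0.71 = 16.1 visible before and 22.7 × 0.90 = 20.4 after.

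**Inputs.** Scan rate s: 0.71 before, 0.90 after (Sample Size Justification). Observed SCT documentation before: 0.53 (same place), read here as the rate among visible infants.

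**Assumptions.** The 71% is for all newborns and is applied to SCT infants, so scanning is taken as unrelated to SCT status. The share of unscanned SCT infants documented from another source, u, is not in the documents. I use 0, 10, 30 and 40%, the same in both periods.

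**Formulas.** With d the documentation rate among scanned SCT infants:

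- observed = (s·d + (1−s)·u) / (s + (1−s)·u)
- all SCT infants = s·d + (1−s)·u

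For each u, d is set so that observed before = 53%. For u = 0.3 the all-SCT rate before is 0.53 × (0.71 + 0.29 × 0.3) = 0.53 × 0.797 = 42.2%, and d = (0.4224 − 0.087) / 0.71 = 47.2%.

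**Scanning rises to 90%, d unchanged.**

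| u | d | Observed, before to after | All SCT infants, before to after |
|---|---|---|---|
| 0 | 53.0% | 53.0% to 53.0% | 37.6% to 47.7% |
| 10% | 51.1% | 53.0% to 51.6% | 39.2% to 47.0% |
| 30% | 47.2% | 53.0% to 48.9% | 42.2% to 45.5% |
| 40% | 45.3% | 53.0% to 47.6% | 43.8% to 44.8% |

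At u = 0 the observed odds ratio is 1.00 against 1.51 for all SCT infants. At u = 30% it is 0.85 against 1.14.

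**How much behaviour change removes the reversal.** Observed after equals 53% when d = 0.53 − 0.1 × u × 0.47 / 0.9. For u = 10, 30 and 40% that is d = 52.5, 51.4 and 50.9%, a rise of 1.4, 4.2 and 5.6 points.

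**At the target, d = 90%.**

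| u | Observed gain | Gain among all SCT infants | Odds ratio, observed / all |
|---|---|---|---|
| 0 | 37.0 points | 81.0 − 37.6 = 43.4 | 8.0 / 7.1 |
| 30% | 37.3 points | 84.0 − 42.2 = 41.8 | 8.3 / 7.2 |
| 40% | 37.4 points | 85.0 − 43.8 = 41.2 | 8.4 / 7.3 |

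**The other reading of 53%.** If it refers to all SCT infants and u = 0, the visible-only baseline is 0.53 / 0.71 = 74.6%. A true post rate below 0.746 × 0.90 = 67.2% would then show as a decline. The mechanism is the same.

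**The case against.** The strongest objection is that the reversal needs a toolkit that hardly works. Changing PCP behaviour is its purpose, and the first table holds that behaviour fixed. This stands. A reader might infer from that table that the SCT result will be hidden or reversed. The documents do not support that: the reversal is gone once documentation among scanned infants rises by 1.4 to 5.6 points, and the planned target is far beyond that.

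Second, the shift is small beside sampling error. With 21 SCT infants per period and rates near 53%, the 95% half-width for the difference is 1.96 × √(2 × 0.53 × 0.47 / 21) = 30 points, before clustering. This stands for any single reading of the pilot. It does not remove a systematic error in the effect size carried forward.

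Third, where the gain comes only from scanning, the scan-rate component would show it, and all-infant fields are already abstracted. That is true, but nothing in the plan says the two are to be read together or that an all-infant SCT rate will be reported.

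Fourth, the denominator is not stated, and 71% is not specific to SCT infants. Both are correct. The first means the bias attaches to a rate over visible SCT infants, the only group the described data can identify. The second means the shift is smaller if SCT results reach charts more often than normal ones.

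**Conclusion.** The concern holds in a limited form. A rate over SCT infants visible in the chart has a denominator that moves with the intervention, and its pre/post odds ratio is biased for the change among all SCT infants. If scanning is unrelated to SCT status, 53% is the rate among visible infants and u lies between 0 and 40%, the pre-period rate is overstated: 53% against about 38-44% of all SCT infants. A modest true gain can be hidden, or reversed by up to about 5 points, if documentation among scanned infants barely changes. At the 90% target there is no reversal: 37 points are seen where about 41-43 occurred, and the odds ratio is about 8 instead of about 7. The scanned-result rate itself, taken over all infants seen, is unaffected.

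**What to change.** Keep the SCT rate among visible infants, but label it as conditional on a visible result. Beside it, pre-specify for each period and arm the number of infants with SCT documented by day 60 over all infants identified, with a confidence interval and the scan rate alongside.

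Add a sensitivity analysis that enlarges the conditional denominator by the expected hidden cases: prevalence × infants with no newborn screen in the chart, less those among them whose SCT is already documented. Use the prevalence observed among scanned infants, by race where possible, or the protocol's 2.1%. In the u = 0 case, 2.1% recovers 37.6% to 47.7%. Giving all unscanned infants 7%, the protocol's figure for African Americans, would show 22% to 39%, a 16-point rise where the true one is 10. This analysis also assumes that scanning is unrelated to SCT status.

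Report the estimates together, and do not make the conclusion depend on their moving in the same direction. For u = 30% with d unchanged, the expected documented SCT counts are 22.7 × 0.422 = 9.6 before and 22.7 × 0.455 = 10.3 after. With Poisson counts the later one is larger 52% of the time, against 45% with no change at all.

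The cost is SAP wording and a few tabulations from fields already abstracted. The drawback is imprecision: the all-infant rate rests on about 10 documented SCT infants per period near the baseline rate.

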For qualitative interviews: During qualitative interviews, a semi-structured format with the interviewer employing a discussion guide composed of open-ended questions will be used. The PI may review selected audiotapes and transcripts of the interviews to monitor the interviewers' performance and to provide further guidance as needed. All interviewers will be trained to handle any emergencies that may arise and to be sensitive to the participants. Each semi-structured interview will be digitally audio recorded and stored on a secure Nemours OneDrive or Sharedrive location only accessible to study staff. Recordings will be labeled with the participant's 3-digit identification code. In the event a name or other identifying information is mentioned during the interview, it will be removed during the transcription process. Digital audio

recordings will be kept until transcription is complete, checked for accuracy and verified, and will then be destroyed.

Control of Bias and Confounding

We anticipate that responses could vary based on social desirability. We will test our survey and interview scripts beforehand in attempt to limit any leading questions. Additionally, we will utilize two coders for qualitative data during analysis to further reduce any reporting or interpretation bias.

Alteration of Consent, Waiver of Documentation of Consent and HIPAA Authorization

We are asking for an alteration of the consent process. Study procedures are brief and minimal/no risk. Requiring inperson communication of busy physicians to provide consent would be disruptive and time intensive during patient care hours (ie business hours) and would be equally burdensome to parents of young infants. To decrease the burden of participation, a virtual, asynchronous consenting process will allow participants to consider study participation while away from patient care hours or child care duties and leisurely consideration of consent documents. All potential participants will have the option to speak with a study team member (coordinator or PI) before consent if desired.

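### Disclosure and free-text note items are scored by manual chart review with no mixed reading order, masking or agreement check, so a change in scoring would be confounded with the pre/post odds ratio

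*Combined protocol and SAP*

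**What the plan says.** Under Statistical Considerations, the primary endpoint is penetration. It covers scanned newborn screening (NBS) results, and documentation and disclosure before 2 months of age in the problem list, medical history and progress note. The timing instruction is "Evaluate monthly: retrospectively (pre intervention) and prospectively (post intervention"). Statistical Methods makes the pre/post comparison primary, using a generalized linear mixed model reported as an odds ratio.

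Study Procedures describes the data collection: "For each infant identified, the following data will be collected via EHR extraction and manual chart review". The list that follows includes "Phase of study they were first seen for a WCC" and "Presence/absence of a disclosure conversation about NBS result in progress notes", the latter with the topics discussed. It does not say which items come from extraction and which from a reader, and it gives no scoring rule for a disclosure conversation.

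On timing, Infant Identification has infants from both periods "identified through EHR data extraction on a rolling basis (i.e. once a month during the trial"). Caregiver Survey Recruitment places identification "at start of the Intervention phase and then every month during the intervention phase) and NBS result reviewed if available in the EHR".

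Control of Bias and Confounding addresses survey and interview wording, and adds that "we will utilize two coders for qualitative data during analysis". Inter-rater reliability appears only under Analysis of Qualitative Data. Neither section mentions chart review.

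**The concern.** Whether a free-text note records a disclosure conversation is a judgement. Readers can become more or less ready to score one as they gain experience, as an abstraction guide is refined, or if they expect the toolkit to work. If pre-period notes are mostly read early and post-period notes later, such a change falls between the two periods being compared. Reading era and study period would then coincide, and neither the PCP and clinic random effects nor any covariate could separate a change in scoring from a change in practice.

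The stake is the estimate more than the test. The Study Objectives give a reliable effect size as the main goal, for use in designing later studies. The plan recognises interpretation by coders as a source of bias for the interviews, but applies no corresponding safeguard to the chart review that feeds the primary endpoint.

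**Working it through.** **The plan's own figures.** Sample Size Justification gives powers of 86% (71% to 90%, n = 74 per period), 85% (20% to 50%, n = 43) and 80% (53% to 90%, n = 21). With h = 2·asin√p2 − 2·asin√p1 and power = Φ(h·√(n/2) − 1.96):

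- n = 74: h = 0.494, power 85.2%
- n = 43: h = 0.644, power 84.7%
- n = 21: h = 0.867, power 80.2%

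The planned 1080 infants also reproduce: 10 PCPs × 54 infants = 540 per arm, and 540 × 2 = 1080. These figures are sound to within rounding and choice of formula. They do not decide this point, which concerns how the outcome is ascertained.

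**Inputs for the illustration**

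- n = 1080 per period and two-sided alpha 0.05: from the plan.
- True rate p = 20% in both periods: assumed. The plan's 20% is for PCP documentation; it gives no baseline for disclosure conversations.
- Reader sensitivity (Se) and specificity (Sp): assumed; the documents give none.
- Infants treated as independent, with no Benjamini-Hochberg adjustment: simplifications.

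**Formula.** Observed rate = Se × p + (1 − Sp) × (1 − p).

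**Case A: readers become readier to score a disclosure** (Se 80% to 90%, Sp 98% to 96%)

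- Pre: 0.80 × 0.20 + 0.02 × 0.80 = 0.176
- Post: 0.90 × 0.20 + 0.04 × 0.80 = 0.212
- Odds ratio = (0.212/0.788) / (0.176/0.824) = 1.26
- Test: difference 0.036, standard error about 0.0170, so Φ(0.036/0.0170 − 1.96) ≈ 56% of trials significant with no true change.

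**Case B: a smaller move the same way** (Se 80% to 85%, Sp 98% to 97%)

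- Pre 0.176; post 0.85 × 0.20 + 0.03 × 0.80 = 0.194
- Odds ratio 1.13; significant about 19% of the time.

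**Case C: readers simply improve** (Se 80% to 90%, Sp 96% to 98%)

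- Pre: 0.80 × 0.20 + 0.04 × 0.80 = 0.192
- Post: 0.90 × 0.20 + 0.02 × 0.80 = 0.196
- Odds ratio 1.03; significant about 6% of the time, close to nominal.

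**Direction.** Running case A backwards (readers become stricter) moves the observed rate from 0.212 to 0.176, an odds ratio of 1/1.26 = 0.79. The bias can therefore hide an effect as well as create one.

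**Clustering.** With an assumed design effect of 2 (effective n = 540 per period), the 56% in case A falls to about 32%. The odds ratio of 1.26 does not change.

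**With a large true effect.** Let the true rate rise from 20% to 50%. A constant reader (Se 80%, Sp 98%) observes 0.176 and 0.80 × 0.50 + 0.02 × 0.50 = 0.410, an odds ratio of 3.25. The drifting reader of case A observes 0.176 and 0.90 × 0.50 + 0.04 × 0.50 = 0.470, an odds ratio of 4.15. Significance is not in doubt either way, but the estimate carried forward differs.

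**The case against.** The strongest reply is that the plan is silent on the workflow, and that silence does not establish a faulty one.

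- **Reading order and reader knowledge.** A reader might infer that retrospective notes are certain to be read first, by staff who know phase and arm. The documents do not say so. The recruitment passage concerns the caregiver survey, and what is reviewed there is the NBS result. The endpoint wording may describe only the periods of the time series. Infant Identification covers both periods without putting one first. This stands: pre-then-post is the natural workflow, not a stated one.
- **Phase on the abstraction form.** A reader might infer this from the data list. The list names variables, not a form, and phase could come from the extraction. This also stands.
- **Scope.** The endpoint is labelled as coming from EHR extraction, and scanned results, problem list and medical history leave little room for judgement. The all-in versus add-in comparison is concurrent, so calendar drift largely cancels, although masking to arm is not stated either. This stands and limits the point to the disclosure and free-text note items. The extraction label does not remove it, because Study Procedures adds manual review.
- **Size.** Cases A and B move both errors in the direction that inflates the post rate; case C shows almost no bias. The plan leaves formal hypothesis testing to later studies and targets much larger shifts. This stands against any emphasis on false positives, but not against bias in the effect size.

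**Conclusion.** The point holds for the disclosure and free-text progress-note items. They are scored partly by manual review, the primary contrast is pre versus post, the natural workflow aligns reading era with period, and no masking, mixed order or agreement check is stated for chart review. If scoring changes, the change enters the primary odds ratio and cannot be modelled out.

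Size and direction are unknown. The spurious odds ratios of about 1.03 to 1.26 rest on the assumed 20% true rate and assumed reader accuracy, and the 56% rejection figure also rests on independent infants. The documents do not support saying that the result will be inflated, or that the whole primary endpoint is compromised. They support saying that a biased effect size is possible in a pilot meant to supply one, and that it is cheap to guard against.

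**What to change.** Keep the monthly extraction and NBS-result review, which the caregiver survey needs. Abstract the disclosure and progress-note items separately, in one pass after the last infant reaches 60 days (the plan's definition of 2 months):

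- Take pre- and post-period charts from both arms in random order.
- Use one abstraction guide, fixed before the pass begins.
- Count only entries dated up to day 60, so that older charts gain nothing from longer follow-up.
- Derive phase and arm from visit date and site, and merge them after abstraction.

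This needs no extra infants, readers or study procedures. The costs are that these data arrive later and some charts are opened twice. Masking will be partial, because notes carry dates and the EHR nudge in the birth history or note template may reveal the phase, so expectation is only reduced. Random order still breaks the link between reading era and study period, which deals with drift.
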